4. * Describe the scientific benefit or importance of the knowledge to be gained:

The benefits of this research are of a scientific nature. Specifically, we aim to use study results to inform our understanding of the abuse liability of ECIG device features/characteristics as well as provide information to guide appropriate regulation of ECIGs. We anticipate long term benefits to the public at large by adding to the limited body of knowledge involving these devices among ECIG only users and dual cigarette and ECIG users.

5. * Describe any potential for direct benefits to participants in this study:

None.

6. Upload a supporting citation list if applicable:

ID: HM20012696

View: SF2 - Study Population

Study Population

1. * Provide the maximum number of individuals that

1. May participate in any study interaction or intervention (Including screening, consenting, and study activities)

AND/OR

2. You obtain any data/specimens about (regardless of identifiability)

at VCU and at other sites under the VCU IRB's oversight. See the help text for additional guidance.
300

2. If this is a multi-Center Project, what is the maximum anticipated number of subjects across all sites?

3. * Provide justification for the sample size by explaining how you arrived at the expected number of participants and why this number is adequate for answering the research questions:

120 completers (60 ECIG exclusive users and 60 Dual ECIG and Tobacco Cigarette users) are required to achieve greater than 80% given $p < 0.05$ for the breakpointMCP and breakpointPRT. We excluded own brand controls to ensure we are powered to detect differences across experimental conditions.

We estimate up to 300 individuals may be consented over the course of the study. Please note that initial telephone/web screening is performed under separate protocols - HM20007677 and HM20002567.

4. * List the study inclusion criteria:

General Inclusion:

Age 21 – 55 (verified by photo ID), willing to provide informed consent, they must agree to attend the lab and abstain from tobacco/nicotine as required and able to provide a semi-quantitative urine cotinine result of 'positive' at screening.

ECIG exclusive Inclusion:

Reports using ≥ 1 ml of ECIG liquid/day or approximately one pod/cartomizer per day of at least 3 mg/ml nicotine for the past 3 months or longer and no tobacco cigarette consumption within the past 30 days.

Dual ECIG and Tobacco Cigarette User Inclusion:

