Overview. This study involves 60 current E-Cigarette (ECIG) only users and 60 Dual Users (ECIG + traditional tobacco cigarette) who will complete 5, within-subject, laboratory conditions that differ by the product used: 1) ECIG with low mg/ml; low watts, 2) ECIG with low mg/ml; high watts, 3) ECIG with high mg/ml; low watts, 4) ECIG with high mg/ml; high watts, and 5) own brand (ECIG or tobacco cigarette). The first ECIG 4 conditions will be Latin-square ordered and single blinded such that the participants will not know which condition is administered in each ECIG session. The last condition for all subjects will be their own brand. For ECIG users it will be their own brand ECIG. For Dual Users it will be either own brand ECIG or tobacco cigarette. To allow for comparisons between groups (ECIG vs Dual) for this own brand condition, we will aim for a majority of the Dual User sample to receive their own brand ECIG in the last session.

Participants. A total of 120 adults (ages 21-55) who currently use ECIGs only or dual ECIG and tobacco cigarettes will be enrolled. We will attempt to recruit an equal number of men and women of diverse racial/ethnic backgrounds, although this study is not intended to address gender or race/ethnic differences.

Inclusion criteria: To be included, participants must be healthy, as determined by self-report and heart rate/blood pressure (HR/BP) check, between the ages of 21-55 (as verified by photo ID), and willing to provide informed consent. They must agree to attend the lab and abstain from tobacco/nicotine as required, to use the designated products, and to follow the study protocol.

Participants must also be either A) ECIG only users [reports using ≥ 1 ml of ECIG liquid/day or approximately 1 pod/cartomizer/day of at least 3 mg/ml nicotine for the past 3 months or longer and no tobacco cigarette consumption within the past month] or B) Dual ECIG + traditional tobacco cigarette smokers [reports daily use of ECIG (≥ 3 mg/ml nicotine) or tobacco cigarettes (any frequency) AND some day use (≥ 3 days per week) of ECIGs (≥ 3 mg/ml nicotine) or tobacco cigarettes (any frequency)] use for the past 3 months or longer] who can provide a semi-quantitative urine cotinine result of 'positive' at screening (urine cotinine cassette test).

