Recruitment and Enrollment. Potential participants will be recruited by IRB-approved advertisements, as well as referral from current participants. Once initial screening is completed (either over the phone or via the internet), potentially eligible participants will earn \$10 to come to the lab for in-person informed consent, screening, and familiarization with study procedures (approximately 1.5 hrs). Prior to in-person data collection, staff will review the informed consent with potential participants to ensure they understand the study, its risks and benefits, and their rights as research participants. Following documentation of informed consent, participants will complete baseline measures to confirm eligibility and provide a urine sample that will be tested for cotinine level (to confirm current smoking status) and pregnancy (women only). Age will be verified by asking participants to provide some form of identification that includes a date of birth. We will also take pictures of their device/liquid. All study procedures will be reviewed and participants will be asked to choose the ECIG liquid flavor to be used during the four study ECIG sessions (i.e., not their own brand session). They will be given the opportunity to test four ECIG liquid flavors using the study ECIG device (tobacco, menthol, dessert, fruit) during screening. After flavor testing, participants will complete the Balloon Analogue Risk Task (BART) and the Minute Discounting Task (counter-balanced administration). Depending upon task performance, participants will receive up to \$40 in compensation for the actual amount earned at the end of the BART task.

New recruits will replace participants who do not complete the study. Accrual ends when the required number of completers (N=120) is reached.

Products. Own brand tobacco cigarette packs or ECIG liquids consistent with participant preference will be purchased locally following enrollment. For all other sessions we will provide ECIG liquid at 10mg or 30 mg nicotine and an "open system" ECIG (i.e., Kanger Sub Box Mini C) set to either 15 watts or 30 watts. Liquid flavors available will include tobacco, menthol, dessert, and fruit.

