Nicotine-related side effects: It is possible that participants may experience unpleasant symptoms associated with over consumption of nicotine during study sessions when tobacco products are administered (e.g., increased heart rate/blood pressure, dizziness, nausea). Importantly, this population will have experience with nicotine consumption. We will exclude individuals at baseline screening that have high blood pressure (meet safety criteria defined below) or withdraw those enrolled if we observe repeated high blood pressure during study sessions (dependent on consultation with medical monitor). The likelihood of these effects is very low. As part of the informed consent process, we will inform participants of potential side effects associated with nicotine consumption.

Our sessions and surveys are optimized in length to make them as short as possible while ensuring collection of primary study outcomes. We believe a 4-hour session and the number of subjective and behavioral assessments per session are not worthy of noting as discomforting.

Though ECIGs will be reused every participant will receive a new disposable mouthpiece that is placed on the ECIG mouthend of the device at each session. Additionally the ECIGs will be cleaned between sessions with rubbing alcohol and water.

Loss of confidentiality is a possibility but we minimize this risk by using a double locked filing cabinet, a password protected database (REDCap) and limiting access to authorized study personnel only. We also assign a unique ID code to participants instead of using their name or other identifiable data to track their participation.

3. * **Describe any potential risks or harms to a community or a specific population based on study findings (e.g. information that could be stigmatizing or derogatory):**
None.

4. **Where appropriate, discuss provisions for ensuring necessary medical, professional, or psychological intervention in the event of adverse events to the subjects:**
Individuals whose BP levels are elevated (≥ 140 mmHg systolic or ≥ 90 mmHg diastolic) during baseline screening will be referred to a primary care provider.

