Title: Effects of E-Cigarette Power and Nicotine Content in Dual Users and Vapers

NCT #: NCT03830892

Document date: 01/21/2020

Document Type: Statistical Analysis Plan

Statistical Analysis Plan

Subjective, physiological, DPT, MCP, and PRT data will be prepared as reported elsewhere ([name] et al., 2017; Rusted et al., 1998; [name] et al., 2010). Elasticity is estimated using an exponential demand function with nonsystematic DTP data excluded based on two criteria: trend, or whether the participant had a general decrease in consumption from the lowest to highest price; and bounce, or whether a participant reported higher consumption at sequential higher prices (Stein et al., 2015). In general, analysis will involve a mixed (between- and within-subject) ANOVA. Demographic data will be examined to determine if there are significant between-group differences on measures that may be related to study outcomes (some differences are expected, like cigarette use). Unexpected between group differences will be considered as potential covariates in the primary analysis (see Evans et al., 2006). For all ANOVAs, adjustments for sphericity violations and post-hoc testing using Tukey's HSD or planned contrasts with Bonferroni corrections will be used (Keppel, 1991). Missing data will be imputed using multiple imputation techniques (Allison, 2001).

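### Does replacing non-completers until 120 have finished, without saying whether the leavers' recorded sessions are analysed, leave the analysis open to bias?

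*Protocol*

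**What the plan says.** The sample-size answer (Protocol, Study Population item 3) counts people who finish: "120 completers (60 ECIG exclusive users and 60 Dual ECIG and Tobacco Cigarette users) are required". It adds "We excluded own brand controls to ensure we are powered to detect differences across experimental conditions". Accrual follows the same count (Study Procedures item 7, Recruitment and Enrollment): "New recruits will replace participants who do not complete the study. Accrual ends when the required number of completers (N=120) is reached".

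In the Overview of item 7, participants are people "who will complete 5, within-subject, laboratory conditions that differ by the product used", and "The last condition for all subjects will be their own brand". The Participants paragraph gives a different unit: "A total of 120 adults (ages 21-55) who currently use ECIGs only or dual ECIG and tobacco cigarettes will be enrolled".

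The Data analysis paragraph and the SAP carry the same text. Both say "In general, analysis will involve a mixed (between- and within-subject) ANOVA", exclude nonsystematic purchase-task data by trend and bounce criteria, and undertake to handle missing data by multiple imputation. Neither says whose data the ANOVA or the imputation covers.

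**The concern.** A conventional mixed ANOVA needs a full row per participant. A trial that counts completers, and replaces everyone else, seems to lead to an analysis of completers alone. Three things would then follow.

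- Recorded sessions would be lost. Own brand is always fifth and lies outside the power calculation. A person who misses only that session has supplied all four powered conditions and might still be replaced.
- The contrasts could be biased if leaving depends on the response to a condition. The Protocol (Risks, Discomforts, Potential Harms and Monitoring, items 2 and 5) allows withdrawal for repeated high blood pressure in sessions, so leaving need not be purely administrative.
- With no analysis set named, the choice could be made after the data are seen.

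The figure of 120 enrolled also cannot hold literally alongside 120 completers once anyone has left.

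**Working it through.** **1. What the text fixes.** The plan's 120 cannot be reproduced, because no effect size, SD or within-person correlation is given. On the question of who is analysed:

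| Text | What it governs | Does it name an analysis set? |
|---|---|---|
| Study Population item 3 | power | no |
| Recruitment and Enrollment | when accrual stops | no |
| Data analysis; SAP: ANOVA | type of model | no |
| Data analysis; SAP: imputation | missing data, with no limit stated | no, but it restricts to no one |
| Data analysis; SAP: trend and bounce | purchase-task data only | the sole stated exclusion |

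Discarding leavers is therefore an inference. The ANOVA and imputation sentences fit together without it: imputation supplies the full rows that the ANOVA needs.

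**2. How many people are involved.** No dropout rate is given, so 5, 10, 20 and 30% are assumed. Starters = 120/(1 − d); leavers = starters − 120. If people leave straight after the strongest condition, and the Latin square puts that condition equally often in positions 1 to 4, each leaver has (1+2+3+4)/4 = 2.5 recorded study sessions on average. A quarter of leavers have all four.

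| d | Starters | Leavers | Recorded study sessions | Leavers with all four |
|---|---|---|---|---|
| 5% | 126.3 | 6.3 | 16 | 1.6 |
| 10% | 133.3 | 13.3 | 33 | 3.3 |
| 20% | 150.0 | 30.0 | 75 | 7.5 |
| 30% | 171.4 | 51.4 | 129 | 12.9 |

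**3. Worst case: completers only, with leaving driven by one condition.** Assumed: participant SD 1, within-person SD 1, normal scores and no true effect. Leaving is logistic in the recorded score of the strongest condition (slope 1 or 2), with low scorers leaving. The nicotine contrast is the mean of two conditions minus the mean of the other two, so its variance is 4 × (1/4) = 1 and its SD is 1. Simulation with 2,000,000 participants gives:

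| Leaving | Completer bias, strongest minus weakest (SD of that contrast) | Completer bias, nicotine (SD) |
|---|---|---|
| 5% | 0.023–0.038 | 0.016–0.027 |
| 10% | 0.045–0.071 | 0.032–0.050 |
| 20% | 0.086–0.130 | 0.061–0.092 |
| 30% | 0.126–0.187 | 0.090–0.133 |

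The sign reverses if high scorers leave. For comparison, the paired effect detectable with 80% power at n = 120 is about (1.960 + 0.842)/√120 = 0.256 SD, or 0.258 from the noncentral t. A bias b shifts the test statistic by b√120. For b = 0.03 the shift is 0.33 and the false-positive rate is 6.2%; for 0.05 it is 0.55 and 8.4%; for 0.09 it is 0.99 and 16.5%.

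**4. The same discard under a more general mechanism.** Let a low score in any session raise the chance of leaving, again with no true effect. The four conditions are then interchangeable, and the square puts each in every position equally often, so completer contrasts are zero by symmetry. Simulation at 5 to 30% leaving gives at most about 0.001 SD. With true effects of 0.25 to 0.5 SD, completers-only shrinks the nicotine effect by 0 to 2% at 5% leaving, 1 to 3% at 10%, 2 to 5% at 20% and 3 to 7% at 30%.

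**5. What an all-sessions model would gain.** If people leave after the session's tasks are recorded, a random-intercept model on all sessions has about zero bias, and its standard error for the nicotine effect is 1 to 9% smaller than with completers alone. If they leave before the tasks are recorded, its nicotine bias is 0.018 to 0.149 SD across 5 to 30% leaving, slightly worse than the completers' 0.016 to 0.133.

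**The case for a change.** The strongest opposing argument is that the silence is real and cheap to end. Two sentences pull in different directions: one counts completers, the other imputes missing data. An analyst could adopt either set after seeing results and claim to follow the plan. At 20 to 30% leaving under the mechanism in step 3, the bias is no longer trivial. A participant with all four powered conditions recorded is a real case whatever the reason for leaving.

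The silence stands; the harm does not follow from it. Replacing someone for accrual is not the same as deleting their data, and the term completer is nowhere defined as four or five sessions. It is also not true that imputation would be idle among completers, because participants may decline questions (Behavioral Intervention Details item 2) and the trend and bounce criteria remove elasticity values. The imputation sentence therefore does not prove that leavers are kept, but it permits it.

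The larger figures depend on dropout rates that no document gives. Payment that is higher in the last session than in the first (Compensation item 2), choice of flavour on the study device, and one permitted repeat of a non-compliant session all work against selective leaving. Nothing links the blood-pressure route to breakpoints.

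**Conclusion.** No change to the plan is needed. The documents leave the handling of replaced participants' sessions unwritten; they do not state a rule that gives a wrong answer. Imputing for all who started is already an allowed reading and should give much the same result as a mixed model on all recorded sessions, since both rely on leaving being explained by recorded data. Preferring one to the other is largely taste.

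Power at 120 completers is unaffected. Any bias requires an unstated discard. Even then it is 0.016 to 0.050 SD for nicotine at 5 to 10% leaving if one condition drives exit, and zero under the any-session mechanism with no true effect. These sizes rest on assumed unit SDs, normal scores, logistic exit and assumed dropout. If dropout proved as high as 20 to 30% and tied to one condition, the choice of set would matter more, but nothing in the documents points there. The figure of 120 enrolled reads as shorthand for 120 finishing, since the sample-size and accrual texts both count completers.

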Procedure. For each session, participants will be asked to refrain from tobacco/nicotine use for ≥ 12 hours and eating food/drinking caffeinated beverages for 1 hour prior to their scheduled session with verification of tobacco/nicotine use status upon arrival at the lab (expired air CO ≤ 7 for ECIG users and ≤ 10 ppm for Dual Users). At the start of the

session, participants rest for 30 minutes, at this time participants will be asked about symptoms experienced since last visit. During this time, participants will not be allowed to use their phones, eat or drink outside beverages but we will provide water to drink and they are invited to read books/magazines or watch movies that we provide to them. Thirty minutes (min) after session onset, participants will sample the session-specific product (2 puffs) followed by a 1 hour rest period, following the same guidelines as the first 30-minute rest period. After the rest period, baseline subjective measures to assess tobacco abstinence symptoms will be completed. Immediately after either the PRT or the DPT/MCP tasks will be completed. The PRT takes approximately 40 minutes to complete and the DPT/MCP takes approximately 40 minutes to complete. Please note that this order, PRT – DPT/MCP or DPT/MCP – PRT, is counterbalanced across participants to control for the effects of completing one task set prior to the other. Following the 1st counterbalanced task assessment, participants will complete a 60-minute rest period. The study procedures should take no more than 240 minutes or 4 hours but study procedures could be completed earlier than that based on decisions the participant makes during the PRT.

0m – CO Check; Physio data collection begins, additional questions about symptoms asked.

30m – 2 puff sample

90m – CO Check; Subjectives measure 1

100m – DPT/MCP OR PRT

140m – Behavioral Measure 1 completed

Subjectives measure 2

Begin 60m rest period

200m – Subjectives measure 3

DPT/MCP OR PRT

240m – Behavioral Measure 2 completed

Subjectives measure 4

end session

Product administration will consist of a 2 sample puff at the beginning of each session. Three behavioral choice tasks will be performed (DPT, MCP, and the PRT). Two of those, (The MCP and the PRT) may yield additional puffs, depending on the decisions made. See the Behavioral Measures section below for more details.

Measures.

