The Minute Discounting Task is a series of hypothetical decision scenarios. Each scenario presents a choice between receiving an amount of money in the present moment or an amount of money at a later time period. These choices are differentiated by option amounts and the time frames. Participants make a choice for five decision scenarios which are automatically adjusted based upon individual responses; while there are approximately 30 potential scenarios, only five are presented to the participant. The task takes less than one minute to complete. This task will only be administered once, during the in person screening.

Physiological measures. Physiological measures are being collected primarily for participant safety during sessions. HR/BP will be measured and saved electronically using software and equipment that sounds an alarm if safety parameters are exceeded (Model 506, Criticare Systems).

Behavioral measures. Our primary behavioral measures are three behavioral choice tasks (Progressive Ratio Task, Drug Purchase Task, and Multiple Choice Procedure).

The Progressive Ratio Task (PRT) requires participants to click on a button on a computer screen 4 times to earn 1 puff of the session specific ECIG. With each additional puff the PRT requires the participant to 'work' twice as hard, in other words after each reward (a single puff) the participant will be required to press the button 8 times, 16 times, 32 times, et cetera for each successive puff. Once the participant declines to press the button for five minutes then the PRT is considered complete.

The Drug Purchase Task (DPT) includes 9 unique measures that assess hypothetical tobacco product purchasing behaviors that are specific to each population (exclusive ECIG user and Dual users) and differ by the session type (experimental ECIG or own brand session). Please see Drug Purchase Task Overview within the attached document. Exclusive users complete 2 or 3 measures for the DPT during each session. Dual users complete 3 or 5 measures for the DPT during each session. DPT measures assess single product purchasing behavior for the session specific ECIG and own brand ECIG/cigarette (1-4; Drug Purchase Task Overview) as well as cross product purchasing behavior between these three products (5-9; Drug Purchase Task Overview) at varying amounts of money. (\$0-\$10.24)

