Importantly these tasks are programmed to end early if participants report zero consumption for assessed products. Estimated time per measure is <3 min, and each measure will only be completed once per session.

The Multiple Choice Procedure (MCP) questionnaire consists of three columns and 15 rows. Ten puffs from the session specific product (session specific ECIG or Own Brand ECIG/Cigarette) will be shown in the center column while varying amounts of money (\$0.01 - \$10.24) will be presented in ascending order in right column. Participants will be instructed to circle whether they prefer puffs or money for each of the 15 choices given to them. The MCP will only be administered once, immediately following the DPT. Immediately after the questionnaire is completed, participants will be presented with one of their choices (drawn randomly) and given a 10-minute 'consumption' period in which to take puffs or receive money. After the consumption period, participants will rest for 10 minutes before either ending the session or beginning the 60-minute rest period.

Subjective measures. Repeatedly within each condition we will use the Minnesota Nicotine Withdrawal Scale and the Direct Effects of Nicotine Scale to measure nicotine withdrawal symptoms before and after each behavioral measure.

Data analysis. Subjective, physiological, DPT, MCP, and PRT data will be prepared as reported elsewhere ([name] et al., 2017; Rusted et al., 1998; [name] et al., 2010). Elasticity is estimated using an exponential demand function with nonsystematic DTP data excluded based on two criteria: trend, or whether the participant had a general decrease in consumption from the lowest to highest price; and bounce, or whether a participant reported higher consumption at sequential higher prices (Stein et al., 2015). In general, analysis will involve a mixed (between- and within-subject) ANOVA. Demographic data will be examined to determine if there are significant between-group differences on measures that may be related to study outcomes (some differences are expected, like cigarette use). Unexpected between group differences will be considered as potential covariates in the primary analysis (see Evans et al., 2006). For all ANOVAs, adjustments for sphericity violations and post-hoc testing using Tukey's HSD or planned contrasts with Bonferroni corrections will be used (Keppel, 1991). Missing data will be imputed using multiple imputation techniques (Allison, 2001).

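### Does leaving the unit and scale of the PRT and MCP breakpoints out of the public plan call for a change?

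*Protocol*

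**What the plan says.** The sample-size answer (Protocol, Study Population, item 3) asks for 120 completers, 60 exclusive e-cigarette users and 60 dual users, to reach more than 80% power at p < 0.05 "for the breakpointMCP and breakpointPRT". It gives no effect size, SD or tested term.

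The tasks are described in Protocol, Study Procedures, item 7. In the PRT the first puff costs 4 clicks and "With each additional puff the PRT requires the participant to 'work' twice as hard". The end rule is: "Once the participant declines to press the button for five minutes then the PRT is considered complete". On duration: "The PRT takes approximately 40 minutes to complete". The MCP has 15 rows running from $0.01 to $10.24, and "Participants will be instructed to circle whether they prefer puffs or money for each of the 15 choices given to them".

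The SAP states that "Subjective, physiological, DPT, MCP, and PRT data will be prepared as reported elsewhere", with citations. Its only task-specific exclusion rules are for the purchase task ("nonsystematic DTP data excluded based on two criteria"). On the model: "In general, analysis will involve a mixed (between- and within-subject) ANOVA". It names no interaction terms and no transformation.

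The hypothesis (Study Procedures, item 1) says that higher power will offset the effect of lower nicotine, and that the nicotine-related reduction will be larger in exclusive users than in dual users.

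**The concern.** The study is powered on two variables whose scoring the reader cannot see. The PRT score could be puffs earned, the last completed ratio or total clicks. The MCP score could be dollars, log dollars or a row number. Nor do the documents say how to score a PRT still running when its slot ends, or an MCP sheet on which the participant switches more than once.

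The unit matters because the hypotheses are relative. The group hypothesis is a group x nicotine interaction, and the offset hypothesis can be read as nicotine x power. Interactions need not survive a change between a raw and a logarithmic scale. If the unit were chosen with the data in hand, that choice could produce or remove the hypothesised result.

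**Working it through.** **The plan's own figure.** The claim of more than 80% power with N = 120 cannot be reproduced, because no effect size or SD is given. At 80% power and two-sided 0.05 (sidedness is my assumption), the detectable effects are:

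- between groups, including a group x nicotine contrast: d = (1.960 + 0.842) x sqrt(2/60) = 0.511;
- within subject, all 120: dz = (1.960 + 0.842)/sqrt(120) = 0.256.

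Both are in SD units, so they apply to whichever scale is used.

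**PRT arithmetic from the stated schedule.** The ratio for puff k is 4 x 2^(k-1). Total clicks for k puffs are 4 x (2^k - 1). The cell values below are illustrations.

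| Pattern | Puffs | Last completed ratio |
|---|---|---|
| Exclusive, 7 to 6 | fall of 1 | 256 - 128 = 128 |
| Dual, 5 to 3 | fall of 2 | 64 - 16 = 48 |
| Low watts, low to high nicotine, 3 to 5 | +2 | 64 - 16 = +48 |
| High watts, low to high nicotine, 5 to 6 | +1 | 128 - 64 = +64 |

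The first pair fails the group hypothesis in puffs and meets it in clicks. The second pair is an offset in puffs and the reverse in clicks. If offset instead means comparing low nicotine/high watts with high nicotine/low watts, the units agree here: 5 v 5 puffs, 64 v 64 clicks.

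**How often this would bite.** These are simulated trials with 60 v 60 participants. All means and SDs are assumptions, since the documents give none.

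- *Means chosen to reverse.* With the 7-to-6 v 5-to-3 pattern and SD 1 between and within persons, the result went significantly against the hypothesis in puffs in 100% of trials and significantly for it in clicks in 85%. The mirror pattern (exclusive 6 to 4, dual 8 to 7) gave opposite significant results in the same data in 84.5%.
- *A modest true interaction in puffs* (+1 v +0.4; between-person SD 1-2, within-person 1-1.5; cap of 8 or 11 puffs). Clicks were significant the wrong way in at most 0.7% of trials. The main cost was power. With dual users 1 puff higher, detection was 58-91% in puffs and 11-52% in clicks. The click range depends on where the assumed mean of 5 puffs is placed; centring the nicotine effect on it gave 7-40%.
- *No interaction, groups at different levels.* When none existed in puffs and groups were 1 puff apart, clicks found one in 5-53%. When none existed in clicks and groups were at 200 v 400, puffs found one in 13-89%. With equal group levels both scales stayed near 5%.
- *Nicotine x power.* Cells of 4, 6, 6, 8 puffs are additive in puffs but give (512 - 128) - (128 - 32) = +288 in clicks, significant in every simulated trial.

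Neither scale wins throughout, so the calculations do not identify a correct one.

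**The 40-minute slot.** Ten puffs need 4 x 1,023 = 4,092 clicks in total, 11 need 8,188 and 12 need 16,380. At an assumed 1 to 7 clicks per second over 35 to 40 minutes, the slot would bind only at 9 to 12 puffs. The tenth puff alone costs 2,048 clicks.

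**MCP.** $10.24/$0.01 = 1,024 = 2^10, so pure doubling gives 11 rows, not 15, and the spacing cannot be inferred. On an assumed doubling ladder one can write down a sign change: steps of 4, 7, 7, 9 give -1 step, but (5.12 - 1.28) - (1.28 - 0.16) = +$2.72. That shows the mechanism on an invented ladder, not a property of this questionnaire.

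**What is already fixed or recoverable.** Puffs, last ratio and total clicks are exact functions of one another, so recording any one recovers the rest. The 15 MCP answers are likewise the raw record. The Protocol's Documents list shows the PRT instrument last modified on 10/16/2018 and the MCP on 1/25/2019, both before the SAP date of 01/21/2020.

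**The case for a change.** The strongest case for a change is this. The protocol calls these tasks primary behavioural measures and powers the study on two of them. The SAP gives explicit data rules for the purchase task and none for these two. A general pointer to cited papers does not say which rule applies to which measure, so an outside reader cannot confirm that the unit was settled beforehand. Stating the unit, the edge-case scores and one scale per outcome would take about five sentences and no new data.

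Much of this stands. The public text gives no unit, crossover rule or scale, and the power statement cannot be checked on any scale. Three parts do not stand. The PRT does have an end rule; only the scoring of a time-truncated run is unstated. The SAP lists no interaction tests, so the sensitive contrasts are inferred from the hypotheses, and the offset can be read as a comparison of two cells. And the remedy favours no scale: if the cited papers or filed instruments already fix the rules, it amounts to copying them across.

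**Conclusion.** No change to the plan follows. The gap is real but is one of documentation: a scoring rule left to cited methods and filed instruments, which analysts can apply without altering the design, the data collected or the sample size. No stated rule is shown to give a wrong answer.

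The possible effect on the PRT is not small. With cell means chosen for the purpose, puffs and clicks disagreed significantly in about 85% of simulated trials. With a modest interaction additive in puffs, reversal was at most 0.7%, and the cost was power. Those figures rest on assumed means, SDs and caps. For the MCP, reversal was written down only on an invented price ladder.

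Harm requires that the unit be both still open and chosen after the data are seen. The documents say neither. The judgement would differ if the cited papers and filed instruments left the unit open; they could not be examined here.
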